11.3 Recording Instructions

11.3.1 Diagnosis

The diagnosis of an AE should be recorded if available. If no diagnosis is available each sign and symptom should be recorded as individual AEs.

11.3.2 Intensity

The investigator will use the NCI-CTCAE version 4.03 to describe the severity of the AE (NCI-CTCAE v4.03, 2010).

The grade assigned by the investigator should be the most severe that occurred during the AE period.

11.3.3 Time of onset

Time of onset for SAEs is the date of appearance of the first symptom of the disease, e.g., if chest pain occurs on 01 April 2015 and the patient is hospitalized with myocardial infarction on 04 April 2015, the onset date is 01 April 2015.

Final 5.0 (incorporating Protocol Amendment 4) 06 Jul 2017

11.3.4 Relationship to Trial Drug

The investigator must assess whether or not the event is related to tisotumab vedotin (HuMax-TF-ADC). If the relationship changes over time, the last judgment by the investigator should be reported. Relatedness has to be assessed and reported from the first time the AE is being reported.

11.3.5 Outcome

Outcome of the AE must be judged by investigator by the following terms:

- Recovered.
- Recovered with sequelae.
- Not recovered.
- Death.
- Unknown.

Instructions for reporting changes in an ongoing AE during a patient's participation in the trial are provided in the instructions that accompany the AE eCRFs.

11.4 Serious Adverse Events

11.4.1 Definition of Serious Adverse Events

Each AE will be classified by the investigator as serious or non-serious. This classification of the seriousness of the event determines the reporting procedures to be followed.

An AE that meets one or more of the following criteria/outcomes is classified as serious:

- Requires inpatient hospitalization or prolongation of existing hospitalization.
- Results in persistent or significant incapacity or substantial disruption of the ability to conduct normal life functions.
- Is a congenital anomaly/birth defect.
- Medically important.
- Results in death.
- Is life-threatening.

The term "life-threatening" in the definition of "serious" refers to an event in which the patient was at risk of death at the time of the event; it does not refer to an event which hypothetically might have caused death if it were more severe.

Elective surgery or other scheduled hospitalization periods that were planned before the patient was enrolled in this trial, as well as scheduled hospitalizations for trial assessments during administration procedures or hospitalizations (or prolongation of existing hospitalization) due to technical or logistical issues, are not to be considered serious. However, the event must be reported on the AE page in the eCRF and commented upon.

Final 5.0 (incorporating Protocol Amendment 4) 06 Jul 2017

Medical and scientific judgment must be exercised in deciding whether an AE is believed to be "medically important". Medically important events may not be immediately life-threatening or result in death or hospitalization but may jeopardize the patient or may require intervention to prevent one of the other outcomes listed in the definition above.

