11 ASSESSMENT AND REPORTING OF ADVERSE EVENTS

11.1 Adverse Events Characterization

11.1.1 Definition of Adverse Events

An AE is any untoward medical occurrence in a patient administered a pharmaceutical product and which does not necessarily have a causal relationship with this treatment.

Adverse events include the following:

- All suspected adverse drug reactions.
- All reactions from medication overdose, abuse, withdrawal, sensitivity or toxicity.
- Apparently unrelated illnesses, including the worsening of a pre-existing illness.
- Injury or accidents. Note that if a medical condition is known to have caused the injury or accident, the medical condition and the accident should be reported as two separate AEs.
- Abnormalities in physiological testing or physical examination findings that require clinical intervention or further investigation.
- Any clinically significant laboratory abnormality suggesting a disease and/or organ toxicity
 and is of a severity that requires active management (i.e., changes of dose, discontinuation
 of drug, more frequent follow-up or a diagnostic investigation), unless they are associated
 with an already reported clinical event.

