11.1.3.1 Pre-existing Conditions

In this trial, a pre-existing condition (i.e., a disorder present before the AE reporting period started and noted on the medical history/physical examination form) should not be reported as an AE. If a pre-existing condition worsens during the treatment period the event should be reported as an AE.

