11.1.4 Procedures

Diagnostic and therapeutic non-invasive and invasive procedures, such as surgery, should not be reported as AEs. A medical condition for which an unscheduled procedure was performed, should however be reported if it meets the definition of an AE. For example, an acute appendicitis should be reported as the AE and not the appendectomy.

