12.4 Statistical Analysis of Primary Endpoint

Incidences of AEs, SAEs, infusion-related AEs, grade \geq 3 AEs, and AEs related to trial drug will be summarized by system organ class and preferred term and listed.

Also, the number of patient days (total number of days in trial) will be shown for each dose group.

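### Section 11.4.1 sends planned surgery and planned or logistical hospital stays to the AE page, against Sections 11.1.1 and 11.1.4, so non-events can enter the all-AE counts (minor)

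*Protocol*

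**What the plan says.** Section 11.4.1 defines serious adverse events and then sets some hospital stays apart. The first kind it names is "Elective surgery or other scheduled hospitalization periods that were planned before the patient was enrolled in this trial". Two further kinds follow: stays arranged for trial assessments, and stays begun or extended for technical or logistical reasons. None of the three counts as serious. The paragraph then ends with an instruction: "However, the event must be reported on the AE page in the eCRF and commented upon".

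Three other sections govern what counts as an AE:

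- Section 11.1.1: "An AE is any untoward medical occurrence in a patient administered a pharmaceutical product".
- Section 11.1.3.1: a condition present before the reporting period is not an AE, with one exception: "If a pre-existing condition worsens during the treatment period the event should be reported as an AE".
- Section 11.1.4: "Diagnostic and therapeutic non-invasive and invasive procedures, such as surgery, should not be reported as AEs". It keeps only the condition behind an unplanned procedure: "A medical condition for which an unscheduled procedure was performed, should however be reported if it meets the definition of an AE".

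AE incidence is the primary endpoint (Section 7.2.1). Section 12.4 summarizes "Incidences of AEs, SAEs, infusion-related AEs, grade" 3 or higher AEs and drug-related AEs by system organ class and preferred term.

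**The concern.** Two instructions in force at the same time tell sites to do different things with the same patient. For elective surgery planned before enrollment, 11.4.1 asks for an entry on the AE page and 11.1.4 forbids one. A stay for trial assessments or logistics is not named in 11.1.4, but it is not an untoward medical occurrence, so 11.4.1 asks for an AE entry for something outside the AE definition.

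Every AE entry also needs an intensity grade, a judgment on relatedness and an outcome (Sections 11.3.2, 11.3.4 and 11.3.5). None of these has a sensible value for a scheduled stay.

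At stake is uniform collection of the primary endpoint. Whether a patient stays in hospital for assessments or logistics depends partly on site practice. If some sites record such stays as AEs and others do not, part of the variation in the all-AE table reflects the recording rule and not the drug.

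**Working it through.** The protocol gives no figure to reproduce, so the check is a comparison of the sections, followed by arithmetic for scale.

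**Step 1: the sections side by side**

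| Item named in 11.4.1 | Under 11.4.1 | Under 11.1.1, 11.1.3.1 and 11.1.4 |
|---|---|---|
| Elective surgery planned before enrollment | Enter on AE page | Do not enter (11.1.4); underlying condition only if it worsened (11.1.3.1) |
| Scheduled stay for trial assessments | Enter on AE page | Not an untoward medical occurrence (11.1.1) |
| Stay, or longer stay, for technical or logistical reasons | Enter on AE page | Not an untoward medical occurrence (11.1.1) |

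The conflict is explicit for surgery. For the two kinds of stay it is with the AE definition.

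**Step 2: which parts of the primary endpoint can move**

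- All AEs, and individual preferred-term rows: exposed.
- SAEs: unaffected, because 11.4.1 itself makes these items non-serious.
- Infusion-related AEs: these need a listed MedDRA term and a judgment of relatedness (11.1.2), so essentially unaffected.
- Grade 3 or higher and drug-related AEs: a planned or logistical stay would not plausibly be given either label, so essentially unaffected.

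**Step 3: scale of one such patient**

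Section 12.3.1 presents incidences as n, % and N patients, so each patient counts once however many entries exist. One patient adds 100 × 1/N percentage points.

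Inputs from Section 8.3: three to six patients per dose level; 20 to 30 expansion patients in two or three arms. With equal arms (an assumption), arm size runs from 20/3 = 6.7, about 7, to 30/2 = 15.

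| Group | N | One patient, points |
|---|---|---|
| Dose cohort, minimum | 3 | 100/3 = 33.3 |
| Dose cohort, expanded | 6 | 100/6 = 16.7 |
| Expansion arm, smallest | 7 | 100/7 = 14.3 |
| Expansion arm, largest | 15 | 100/15 = 6.7 |
| All expansion patients | 20 to 30 | 100/20 = 5.0 to 100/30 = 3.3 |

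A preferred-term row created by such an entry moves by these amounts. The any-AE row moves only if the patient has no other AE. Since Section 11.2 requires all AEs to be reported whatever their cause, that will be uncommon.

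**Step 4: how often the items can arise**

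Exclusion criterion 13 bars patients with major surgery planned during treatment. The protocol schedules no inpatient stay: the flow charts ask for at least 2 hours in hospital after an infusion, and longer only at the investigator's discretion. In Dose Escalation, next-day sampling follows only Days 1 and 15 of Cycle 1 (Table 2, Days 2 and 16). On the three-weekly schedule, sampling is on Days 1, 8 and 15 (Table 6), which gives no reason for an overnight stay.

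**The case against.** The best defense is that the event in the disputed sentence means an AE. Section 11.4.1 opens by classifying AEs as serious or not and uses the word in that sense. On this reading the paragraph says only that a planned or logistical stay does not make an AE serious, while the AE itself is still recorded. That would match 11.1.4, which reports the condition and not the procedure.

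This does not rescue the sentence. The condition behind surgery planned before enrollment is normally pre-existing, and 11.1.3.1 excludes it unless it worsens. A stay for assessments or logistics has no underlying condition, so an instruction that its event must be entered can refer only to the stay. Section 11.4.2.2 shows how the protocol words this elsewhere: an overdose is reported as a protocol deviation and goes on the AE page only if an AE results. Section 11.4.1 lacks that condition.

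Two parts of the defense do stand. The comment that 11.4.1 requires may make such entries identifiable later, and a rule for the tables could sit in the SAP, which is not shown. Neither makes collection uniform across sites.

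A reader might also infer that a stay around every infusion would fill the AE tables and push any-AE incidence to its ceiling regardless of the drug. The documents do not support this. No stay is scheduled, next-day sampling is confined to two days of one cycle in one part of the trial, and repeated entries in one patient count once.

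**Conclusion.** The contradiction is real and stands in the current text. It is direct for planned surgery, and it runs through the AE definition for planned and logistical stays. The severity is minor.

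Exposure is confined to the all-AE count and preferred-term rows. One affected patient shifts such a row by 33 points at n=3, 17 at n=6, and about 7 to 14 in an expansion arm. The total effect is probably small because the items should be rare and most patients will have another AE. The other primary-endpoint components are essentially unchanged.

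This rests on three assumptions: at least some sites apply 11.4.1 literally, the entries are not removed before analysis (the protocol states no such step), and expansion arms are about equal in size. The documents do not show that non-events have been or will be counted; they show that the written rules allow it.

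**What to change.** Reconcile 11.4.1 with 11.1.1, 11.1.3.1 and 11.1.4 by replacing the last sentence of that paragraph with wording such as: *Such surgery and hospital stays are not in themselves AEs and are not entered on the AE page. An accompanying medical condition that is new or has worsened is reported as an AE according to Sections 11.1.3.1 and 11.1.4.* Carry the same line into the eCRF completion guidelines.

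For entries already made, list those that record only planned surgery or a planned or logistical stay, and exclude them from the AE incidence tables.

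The cost is one protocol sentence, one line in the guidelines and one rule for the tables. No new data are collected, and any true untoward event is still captured.

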11.4.2 Events Requiring Immediate Reporting

11.4.2.1 Serious Adverse Events, Non-serious Grade 3 Adverse Events, and Non-serious Grade 2 Ocular Adverse Events

Serious adverse events and non-serious grade 3 AEs will be reported from the investigational site to the sponsor within 24 hours (see Sections 10.9 and 11.4.3). In addition, all non-serious grade 2 ocular AEs must be reported from the investigational site to the sponsor within 24 hours (see Section 11.4.3).

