8.4.5.2 Dose Modification for Peripheral Neuropathy and Neutropenia

Peripheral neuropathy should be managed using a combination of dose delay and reduction to 2/3 of the initial dose:

- For new or worsening CTCAE grade 2 or 3 neuropathy: hold dose until neuropathy improves to CTCAE grade ≤ 1, and then restart at 2/3 of the initial dose until end of trial treatment.
- For CTCAE grade 4 peripheral neuropathy: stop dosing and the patient should be withdrawn from treatment.

Neutropenia should be managed by dose delays and dose reductions:

- Dosing should be held for CTCAE grade 3 or 4 neutropenia until resolution to CTCAE grade ≤ 2.
- Growth factor support should be considered for subsequent cycles in patients who experience CTCAE grade 3 or 4 neutropenia.
- In patients with recurrent CTCAE grade 4 neutropenia despite the use of growth factors, discontinuation or dose reduction of trial drug to 2/3 of the initial dose until end of trial treatment may be considered after discussion with the sponsor Medical Officer.

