10.9 Adverse Events

Adverse events will be assessed and reported at each visit. All AEs will be graded according to the NCI-CTCAE version 4.03 (NCI-CTCAE v4.03, 2010).

SAEs and non-serious grade 3 AEs will be reported from the investigational site to the sponsor within 24 hours. In addition, all non-serious grade 2 ocular AEs must be reported from the investigational site to the sponsor within 24 hours.

Weekly Safety/Medical meetings will be held in the Dose Escalation part of the trial to evaluate all AEs and laboratory data and follow-up information obtained during the previous week. In the Cohort Expansion part of the trial, bi-weekly evaluations will be made.

Further details on AEs monitoring and reporting are provided in Section 11.

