10.16 Laboratory Assessments

Blood sampling will be collected for assessment of laboratory parameters. Some laboratory samples will be tested at the site while others will be drawn and shipped for centralized testing.

A manual with detailed description of the procedures for sampling, handling, storage and shipment of the laboratory samples and all material such as test tubes and labels for central analysis will be provided by the central laboratory. The manual and the result reports will include all reference ranges.

Laboratory equipment in central and local laboratories may provide standard analyses not requested in the protocol but produced automatically in connection with the requested analyses. Such data will not be transferred to the eCRF but must be reported to the investigator.

If a non-serious grade ≥ 3 laboratory abnormality occurs during Cycle 1 and is assessed as related or possibly related to the trial drug, then a new laboratory sample should be collected performed within 48 hours (and as close to 48 hours as possible) and reported as an unscheduled visit. This is to confirm or reject the fulfillment of the DLT assessment as defined in Section 8.4.8 (Any grade ≥ 3 non-hematological AEs which occur during the first treatment cycle and are at least possibly trial drug related, excluding non-hematological laboratory abnormalities that have no clinical consequences and resolve within 48 hours).

Final 5.0 (incorporating Protocol Amendment 4)

A patient can always be called in for an unscheduled visit(s) if judged necessary by the investigator.

To monitor patient safety, the investigator can request additional blood samples at the unscheduled visit. The reason for the visit and visit date must be recorded in the eCRF.

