11.5 Follow-up on Adverse Events

All AEs should be followed until they are resolved or the patient's participation in the trial ends, whichever comes first. Related non-serious grade ≥ 3 AEs and AEs meeting one of the serious criteria, and still ongoing after ended trial participation should be followed on a regular basis, according to the investigator's clinical judgment, until the event has been resolved or until the investigator assesses it as chronic or stable and all queries have been resolved.

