11.6 Safety Communication Plan for Information to Site

In order to secure full transparency regarding patient safety-related questions to sites participating in the trial, frequent communication of observations at the different sites will be required. The communication set-up will include the following components:

- SAEs, non-serious grade 3 AEs and non-serious grade 2 ocular AEs will be reported by the investigational site to the sponsor within 24 hours and medically evaluated immediately following receipt. Bi-weekly safety/medical meetings to discuss AEs and laboratory data will be held with the participation of at least the Corporate Drug Safety, Genmab Medical Officer and CRO Medical Monitor.
- Recruitment updates will be prepared by the CRO for sites and investigators including information on all SAEs, non-serious grade 3 AEs, non-serious grade 2 ocular AEs and DLTs.

Final 5.0 (incorporating Protocol Amendment 4)

- Monthly telephone conferences between all participating investigators, CRO Medical Monitor and Genmab will be arranged. Pending severity of observed safety signals, ad hoc meetings will be held.
- A contact list with all participating investigators will be available at all sites.
- 24 hours/7 days a week availability of CRO Medical Monitor.
- Direct telephone link from investigator to Genmab Medical Officer and responsible Genmab Drug Safety Physician.
- DMC meetings following each cohort and ad hoc as needed. The outcome of the DMC meeting will be communicated to the investigators following each meeting.
- Investigators or their representative(s) will participate in the open part of the DMC meetings as applicable.

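### The 24-hour reporting rule names non-serious grade 3 events but not grade 4, so a non-serious grade 4 event has no expedited timeframe or form while a milder one does

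*Protocol*

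**What the plan says.** The expedited-reporting rule is given in five places in the protocol, each time with the same event categories.

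- Section 11.4.2.1: "Serious adverse events and non-serious grade 3 AEs will be reported from the investigational site to the sponsor within 24 hours". It adds that "all non-serious grade 2 ocular AEs must be reported from the investigational site to the sponsor within 24 hours".
- Section 10.9: "SAEs and non-serious grade 3 AEs will be reported from the investigational site to the sponsor within 24 hours".
- Section 11.4.2.2 applies the same categories to adverse events that result from an overdose, and refers medication errors back to 11.4.2.1.
- Section 11.4.3 with Table 9 has four rows: SAEs, grade 3 AEs, grade 2 ocular AEs and pregnancy. The grade 3 row has its own form, titled for non-serious grade 3 events.
- Section 11.6 repeats the site-to-sponsor duty and says what is passed on to other sites: "Recruitment updates will be prepared by the CRO for sites and investigators including information on all SAEs, non-serious grade 3 AEs", followed by grade 2 ocular events and DLTs.

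Two other sections use a wider category. Section 11.5, on follow-up after trial participation, speaks of "Related non-serious grade ≥ 3 AEs and AEs meeting one of the serious criteria". Section 10.16, on repeat sampling, begins: "If a non-serious grade ≥ 3 laboratory abnormality occurs during Cycle 1".

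**The concern.** An expedited rule should not become less demanding as severity rises. Here a non-serious event has to reach the sponsor within 24 hours at grade 3 (or at grade 2 if ocular), but the text imposes no such duty at grade 4 unless another criterion is met.

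This matters because the listed reports feed two safety processes in Section 11.6: prompt medical evaluation by the sponsor, and the CRO updates to the other sites. Non-serious grade 4 events are not among the categories for either. Adverse events are the primary endpoint, and grade 4 neutropenia is a foreseen toxicity with its own provision in Section 8.4.5.2, which opens "In patients with recurrent CTCAE grade 4 neutropenia despite the use of growth factors".

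**Working it through.** No arithmetic applies. The check sets the reporting rule beside the definitions that decide whether a grade 4 event could reach the sponsor within 24 hours by another route.

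**Step 1: is grade 4 always serious?** No. Section 11.4.1 makes seriousness, not grade, determine the reporting procedure. An event counts as life-threatening only if the patient was actually at risk of death when it occurred. Table 7 defines grade 4 neutropenia by the count alone (ANC below 0.5 × 10⁹/L), and grade 4 thrombocytopenia likewise. A patient can meet either cut-off without meeting a seriousness criterion, unless the investigator judges the event medically important.

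**Step 2: does the protocol recognise the category?** Yes. Sections 10.16 and 11.5 both write non-serious together with grade ≥ 3.

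**Step 3: can such an event be an AE?** Yes. Section 11.1.1 includes clinically significant laboratory abnormalities that need active management, and Section 8.4.5.2 calls for dosing to be held at grade 3 or 4 neutropenia.

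**Step 4: which 24-hour routes exist, as written?**

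| Event | 24-hour duty | Source |
|---|---|---|
| SAE, any grade | Yes, SAE form | 11.4.2.1, Table 9 |
| Non-serious grade 3 AE | Yes, own form | 11.4.2.1, Table 9 |
| Non-serious grade 2 ocular AE | Yes, own form | 11.4.2.1, Table 9 |
| Grade 4 event meeting Table 7, Cycle 1, Dose Escalation | Yes, as a DLT | 8.4.8 |
| Other non-serious grade 4 AE, Cycle 1, Dose Escalation | None stated | – |
| Non-serious grade 4 AE, later cycles, Dose Escalation | None stated | – |
| Non-serious grade 4 AE, any cycle, Cohort Expansion | None stated | – |

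**Step 5: how far does the DLT duty reach?** Section 8.4.8 is limited to the Dose Escalation part and to the first 28-day cycle. Within that window Table 7 covers grade 4 neutropenia lasting at least 7 days, febrile neutropenia of grade 3 or 4 with no duration condition, and grade 4 thrombocytopenia on the count alone. Afebrile grade 4 neutropenia shorter than 7 days is not covered.

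**Step 6: what else operates in the Cohort Expansion part?** Section 11.7 plans no DMC meetings there, although the committee convenes on a new safety signal. Sections 10.9 and 11.6 provide bi-weekly safety reviews.

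**The case against.** Several points on the other side have weight.

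- **Medically important events.** Section 11.4.1 lists this as a separate seriousness criterion. An investigator may well apply it to grade 4 neutropenia, and the event then goes on the SAE form within 24 hours. This shrinks the uncovered set. It does not remove it, because the criterion rests on individual judgment and may be applied differently from site to site.
- **Other sponsor contacts.** Section 8.4.5 asks for Medical Officer preapproval of dose modifications, 8.4.5.5 for contact before the next dose after grade ≥ 3 liver-enzyme events, and 8.4.5.2 for discussion in recurrent grade 4 neutropenia. Section 11.6 offers a CRO Medical Monitor at all hours. None of these sets a 24-hour limit or uses the reporting forms. They do mean that the sponsor may learn of an event well before a scheduled review.
- **Different purposes.** Sections 10.16 and 11.5 govern repeat sampling and follow-up, so they do not directly contradict the reporting rule. They show that the category exists and that the rule omits it.
- **Trial procedures manual.** Section 11.4.3 refers to a manual that is not available here and may instruct sites on grade 4. If so, it would be correcting a protocol rule that reads otherwise in five places.
- **No effect on the analysis.** Non-serious AEs are still recorded at visits, and grade ≥ 3 events are summarised in the primary endpoint. This is correct: the defect concerns the timeliness of safety oversight, not estimation.

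**Conclusion.** The gap is real. As the protocol is worded, a non-serious grade 4 AE has no expedited timeframe or form while a non-serious grade 3 AE has both. It is widest in the Cohort Expansion part, where it applies to every cycle in 20 to 30 planned patients. The conclusion assumes that sites follow the text literally and that the event has not been judged serious. The likely intent was grade ≥ 3.

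Three stronger readings are tempting, but the documents do not support them.

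- A reader might infer a delay of about 14 days from the bi-weekly reviews. The term is not defined, and the other sponsor contacts could bring the event to light sooner, so no delay can be derived.
- A reader might illustrate the anomaly with a specific ANC value for grade 3. The protocol gives only the grade 4 cut-off, and a laboratory value is an AE only under the conditions of Section 11.1.1.
- A reader might conclude that SAEs and grade 3 events are the only ones with a 24-hour duty, or that neutropenia is a DLT only after 7 days. Grade 2 ocular events, pregnancies, overdoses and DLTs also carry 24-hour duties, and febrile neutropenia is a DLT without a duration condition.

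The protocol does not say how many events would be affected.

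**What to change.** Replace non-serious grade 3 with non-serious grade ≥ 3 in Sections 10.9, 11.4.2.1, 11.4.2.2, 11.4.3 with Table 9, and 11.6, including the list of events in the CRO updates. Rename the report form to match. The wording then agrees with Sections 10.16 and 11.5. If the trial procedures manual repeats the rule, it should be aligned as well.

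The cost is a text change, a new form title and a few additional expedited reports. No dose, treatment or analysis rule is affected.
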